#### 8.1.14 Adverse events with lenalidomide

The most frequently reported adverse events reported during clinical studies with lenalidomide in oncologic and non-oncologic indications, regardless of presumed relationship to study medication include: anemia, neutropenia, thrombocytopenia and pancytopenia, abdominal pain, nausea, vomiting and diarrhea, dehydration, rash, itching, infections, sepsis, pneumonia, UTI, Upper respiratory infection, cellulitis, atrial fibrillation, congestive heart failure, myocardial infarction, chest pain, weakness, hypotension, hypercalcemia, hyperglycemia, back pain, bone pain, generalized pain, dizziness, mental status changes, syncope, renal failure, dyspnea, pleural effusion, pulmonary embolism, deep vein thrombosis, CVA, convulsions, dizziness, spinal cord compression, syncope, disease progression, death not specified and fractures.

Complete and updated adverse events are available in the Investigational Drug Brochure and the IND Safety Letters.

## 8.2 13-valent Protein-Conjugated Pneumococcal Vaccine (Prevnar 13, PCV13)

### 8.2.1 Supplier(s)

PCV13 is manufactured by Wyeth Pharmaceuticals and is commercially available.

### 8.2.2 Description

PCV13 is a sterile suspension of saccharides of the capsular antigens of *Streptococcus pneumoniae* serotypes 1, 3, 4, 5, 6A, 6B, 7F, 9V, 14, 18C, 19A, 19F, and 23F, individually linked to non-toxic diphtheria CRM197 protein. Each serotype is grown in soy peptone broth. The individual polysaccharides are purified through centrifugation, precipitation, ultrafiltration, and column chromatography. The polysaccharides are chemically activated to make saccharides, which are directly conjugated by reductive amination to the protein carrier CRM197, to form the glycoconjugate. CRM197 is a nontoxic variant of diphtheria toxin isolated from cultures of *Corynebacterium diphtheriae* strain C7 (β197) grown in a casamino acids and yeast extract-based medium. CRM197 is purified through ultrafiltration, ammonium sulfate precipitation, and ion-exchange chromatography. The individual glycoconjugates are purified by ultrafiltration and column chromatography and analyzed for saccharide to protein ratios, molecular size, free saccharide, and free protein.

The individual glycoconjugates are compounded to formulate PCV13. Potency of the formulated vaccine is determined by quantification of each of the saccharide antigens and by the saccharide to protein ratios in the individual glycoconjugates. Each 0.5 mL dose of the vaccine is formulated to contain approximately 2.2 µg of each of *Streptococcus pneumoniae* serotypes 1, 3, 4, 5, 6A, 7F, 9V, 14, 18C, 19A, 19F, 23F saccharides, 4.4 µg of 6B saccharides, 34 µg CRM197 carrier protein, 100 µg polysorbate 80, 295 µg succinate buffer, and 125 µg aluminum as aluminum phosphate adjuvant.

#### 8.2.3 **Packaging**

PCV13 is supplied as 0.5 mL single-dose pre-filled syringes for intramuscular injection, with 10 doses per package (NDC 0005-1971-02). The vial stopper and the tip cap and rubber plunger of the pre-filled syringe do not contain latex.

#### 8.2.4 **Storage and stability**

The product is a suspension containing an adjuvant and should be vigorously shaken prior to use. Unopened containers should be stored at 2-8°C and unused portions discarded. PCV13 should not be frozen and should be discarded if frozen.

#### 8.2.5 **Contraindications**

Known hypersensitivity to PCV7, PCV13, or to any of the components of the conjugate vaccine.

#### 8.2.6 **Adverse effects**

Local reactions include erythema, induration, and tenderness. Other adverse reactions include fever, irritability, drowsiness, restless sleep, decreased appetite, vomiting, diarrhea, urticaria-like rash, lymphadenopathy localized to the region of the injection site, hypersensitivity reactions including face edema, dyspnea, bronchospasm, and anaphylactoid reactions, angioneurotic edema, and erythema multiforme.

#### 8.2.7 **Administration guidelines**

Since this product is a suspension containing an adjuvant, it should be vigorously shaken immediately prior to use to obtain a homogenous, white suspension in the vaccine container. If it cannot be resuspended, the product should not be used. It should not be used if particulate matter or discoloration is found on visual inspection. It should not be mixed with any other vaccines/products in the same syringe. A 0.5 ml dose is given intramuscularly in the deltoid muscle of the upper arm. It should not be administered intravenously, intradermally, or subcutaneously. Patients will receive 2 doses of PCV13 administered 8 weeks apart. In Arm A (Concurrent), vaccine will be administered on Day 1 of cycles 3 and 5. In Arm B (Sequential), patients will be vaccinated on Day 1 of cycles 1 and 3.

### **9. CORRELATIVE/SPECIAL STUDIES**

The rich biology associated with lenalidomide administration in CLL offers the opportunity to perform detailed correlative studies. These studies are outlined below. Outside of studies outlined in [\*\*Section 9.1\*\*](#) which are related to the study primary endpoint, collection times or samples may be deleted or altered (with no excess draws or collection from this baseline) if deemed to be impractical. If this occurs, an amendment will be

submitted related to this but accrual to the study will not be interrupted while this is under review.

Study end points have been met, therefore all research sample collection will cease upon approval of protocol version 24. Given the low number of patients continuing to receive treatment additional research samples will not be of scientific interest.

## **9.1 Anti-pneumococcal Antibody Levels**

Specimens collected for anti-pneumococcal antibody levels will be processed in the OSU CLL Experimental Therapeutics Laboratory prior to shipment to a contract laboratory (Mayo Medical Laboratories, Rochester, MN) where type-specific antibody levels will be measured.

### **9.1.1 Collection of Specimens**

In Arm A (Concurrent), serum antibody levels specific to each of 7 pneumococcal antigens contained in the PCV13 vaccine will be assessed at Cycle 1 Day 1 (baseline), 2 months following initiation of lenalidomide therapy (Cycle 3 Day 1), 2 months after initial vaccination (Cycle 5 Day 1) and 1 month after second vaccination (Cycle 6 Day 1) and every 6 months thereafter for patients remaining in follow-up. For those in Arm B, titers will be assessed at Cycle 1 Day 1(baseline), 2 months after initial vaccination (Cycle 3 Day 1), 1 month after second vaccination (Cycle 4 Day 1), and every 6 months thereafter.

### **9.1.2 Handling of Specimens**

One 5 mL of blood will be collected in plain red top tubes, mixed 5 times and allowed to clot 30 minutes. Samples will then be spun at 1,200 x g for 10 minutes to isolate serum. Serum in three separate vials will be stored in -80°C freezer. Each sample will be labeled with the protocol number, patient number, reference time point relative to the protocol, date and time the sample was obtained, and date and time the sample was placed in the -80°C freezer until further analysis. 0.5 mL of refrigerated serum sent to the Mayo Medical Laboratories, Rochester, MN, as outlined in the laboratory manual. Additional serum remaining may be used for other tests related to understanding mechanism of action/response of lenalidomide or biology of CLL.

### **9.1.3 Sample and Data Analysis.**

IgG antibodies to *Streptococcus pneumoniae* serotypes are measured by microsphere photometry. Purified pneumococcal polysaccharides coupled covalently to polystyrene microspheres bind IgG antibodies in patients' sera during the first incubation. After incubation, the microspheres are washed and incubated with phycoerythrin conjugated antihuman IgG antibody. The concentration of IgG antibodies to each polysaccharide is determined by comparison to dose-response curves calculated from serial dilutions of a serum pool from immunized adults with known concentrations of antibodies to each polysaccharide (secondary standard). The secondary standard is traceable to a standard reference preparation (FDA 89-SF) that contains known concentrations of IgG antibodies to 23 different *Streptococcus pneumoniae* serotypes. Dose-response curves prepared from

serial dilutions of the secondary standard parallel the dose-response curves of the primary reference preparation for all polysaccharides. (Jacob GL, Homburger HA: Simultaneous Quantitative Measurement of IgG Antibodies to *Streptococcus Pneumoniae* Serotypes by Microsphere Photometry. Poster Presentation; AAAAI 60th Annual Meeting, March 19-23, 2004. San Francisco, CA. J Allergy Clin Immunol, Vol. 113, No 2, [Abstract 1049, pS288] 2004; Plikaytis BD, Holder PF, Pais LB, et al: Determination of parallelism and nonparallelism in bioassay dilution curves. J Clin Microbiol 1994;2441-2447; Plikaytis BD, Goldblatt D, Frasch CE, et al: An analytical model applied to a multicenter pneumococcal enzyme-linked immunosorbent assay study. J Clin Microbiol 2000;38:2043-2050)

## **9.2 Pharmacodynamic Studies: Immunoglobulins and Anti-Tumor Antibodies**

Pharmacodynamic studies concerning serum immunoglobulin and anti-tumor antibody levels will be performed at the OSU CLL Experimental Therapeutics Laboratory in collaboration with [name] of the NCI intramural research program.

### **9.2.1 Collection of Specimens**

For patients treated on Arm A (patients who receive lenalidomide beginning Cycle 1, collection of blood samples will occur on Days 1 (baseline), and Day 1 of 3, 5, 7 and every 6 months subsequently. For patients treated on Arm B (patients who receive lenalidomide beginning with Cycle 4), samples will be collected at Day 1 of Cycle 1 (baseline), Day 1 of Cycles 4, 5, 7, and every 6 months subsequently.

### **9.2.2 Handling of Specimens**

Two x 5 mL of blood will be collected in plain Red top tubes, mixed 5 times and allowed to clot 30 minutes. Samples will then be spun at 1,200 x g for 10 minutes to isolate serum. Serum in three separate vials will be stored in -80°C freezer. Each sample will be labeled with the protocol number, patient number, reference time point relative to the protocol, date and time the sample was obtained, and date and time the sample was placed in the -80°C freezer until further analysis.

### **9.2.3 Sample and Data Analysis.**

The samples will be analyzed in batches to assess quantitative total and vaccine specific immunoglobulin levels as outlined below. Levels of immunoglobulin levels over time will be correlated with the ability of lenalidomide to up-regulate CD154 on CLL cells and pharmacokinetics of lenalidomide.

- **Anti-IgG1, IgG2, IgG3, IgG4, IgM, and IgA** will be determined from serum at baseline and every 6 months thereafter on select patients for whom reversal of hypogammaglobulinemia occurs.
- **Anti-ROR1 antibody levels:** Tumor-specific anti-ROR1 antibody titers will be determined by ELISA in serum at baseline and every 6 months thereafter. Development of ROR1 antibodies will be correlated with the ability to up-regulate CD154 on CLL cells and pharmacokinetics of lenalidomide
- **Anti-CLL tumor antibody levels:** Tumor-specific antibody titers will be determined

by an adapted flow cytometry assay from serum at baseline and every 6 months thereafter. Development of anti-CLL antibodies will be correlated with the ability to up-regulate CD154 on CLL cells and pharmacokinetics of lenalidomide. In patients developing such antibodies, normal B-cells derived from these patients will be isolated for identification of relevant target antigens. This will be done in collaboration with [name].

### 9.3 Lenalidomide Pharmacokinetics

Pharmacokinetic evaluations for lenalidomide will be conducted in collaboration with the Pharmacooanalytical Shared Resource at OSU.

#### 9.3.1 Collection of Specimens.

**Arm A:** For patients treated on Arm A (patients who will receive lenalidomide during cycles 1 and 2), pharmacokinetic assessments of lenalidomide will occur during days 1 and 2 of cycle 2. Samples will be collected at the following time points: prior to dosing (time 0), 0.5, 1, 2, 3, 4.5, and 6 hours after dose administration on day 1 of cycle 2. An additional sample will be obtained prior to lenalidomide ingestion on day 2 of cycle 2 (i.e. 24 hours after the dose is ingested on day 1).

**Arm B:** For patients in Arm B (patients who receive lenalidomide beginning in cycle 4) PK sampling will occur during days 1 and 2 of cycle 5. The sampling times will be consistent with those in Arm A and comprise the following time points: prior to dosing (time 0), 0.5, 1, 2, 3, 4.5, and 6 hours after dose administration on day 1 of cycle 5. An additional sample will be obtained prior to lenalidomide ingestion on day 2 of cycle 5 (i.e. 24 hours after the dose is ingested on day 1).

#### 9.3.2 Handling of Specimens.

Four mL of blood will be collected in EDTA (purple top) tubes, placed on ice and immediately centrifuged at 1,200 x g for 10 minutes to isolate plasma. Plasma will be frozen in two separate vials and stored in a -20°C freezer. Each sample will be labeled with the protocol number, patient number, reference time point relative to the protocol, date and time the sample was obtained, and date and time the sample was placed in the -20°C freezer.

#### 9.3.3 Sample and Data Analysis.

The samples will be analyzed in batches to assess plasma drug concentrations, the plasma drug concentration-time profile (AUC), volume of distribution (Vss), clearance (CL), and half-life using liquid chromatographic/mass spectrometry (LC/MS) according to previously described methods. Comparisons of PK data from patients treated on Arm A

vs. Arm B will be made to assess possible PK alterations due to PCV13 administration. Additional comparisons will be made between patients who received dexamethasone treatment on cycles 1 (Arm A) or 5 (Arm B) to identify potential interactions between lenalidomide and dexamethasone due to steroid-induced induction of MDR1 or other lenalidomide clearance mechanisms.

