**Table 2: Lenalidomide Dosing and Administration**

Treatment Arm	Cycle	Dose	Ancillary Medications	Schedule	Cycle Length
A Concurrent	1	2.5 mg/day	Allopurinol 300 mg/day beginning 3 days prior to lenalidomide and continuing through at least the end of Cycle 1	Days 1-28 continuous	28 days
	2+	5 mg/day	Dexamethasone may be given for up to 7 days during Cycles 1 and 2 for symptomatic tumor flare		

B Sequential	1-3	No lenalidomide	Allopurinol 300 mg/day beginning 3 days prior to lenalidomide and continuing through at least the end of Cycle 4  Dexamethasone may be given for up to 7 days during Cycles 4 and 5 for symptomatic tumor flare	Days 1-28 continuous	
	4	2.5 mg/day			
	5+	5 mg/day			

Lenalidomide dosing and administration are summarized in **Table 2**. Lenalidomide treatment will be administered at 2.5 mg/day during the first cycle of treatment (Arm A: Cycle 1; Arm B: Cycle 4) to minimize risks for tumor flare and/or tumor lysis. The dose of lenalidomide will be increased to 5 mg/day beginning as early as the second cycle of therapy (Arm A: Cycle 2; Arm B: Cycle 5) if all of the following criteria are met on Day 1:

- No clinically significant Grade 3 or greater non-hematologic toxicities attributable to lenalidomide during the preceding cycle.
- Any hematologic toxicity is resolved to  $\leq$  Grade 1.
- Maintained platelet count  $>50K$  at all times during the previous cycle.
- Maintained ANC  $>1K$  at all times during the preceding cycle.
- Any other drug-related adverse events have resolved to Grade  $\leq 1$  severity.

During the first cycle of lenalidomide exposure, and any cycle in which the dose is subsequently escalated, patients are seen on Days 1 and 8 for laboratory evaluation (CBC, chemistries), history, and physical examination to evaluate for tumor lysis and/or tumor flare, respectively. Management of tumor flare response is detailed in **5.2.1** below.

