## 5.2 General Concomitant Medication and Supportive Care Guidelines

Patients should receive full supportive care, including transfusions of blood and blood products, antibiotics, and antiemetics when appropriate. All concomitant medications, including the reason(s) for treatment, dosage, and the dates of treatment, should be recorded on the flow sheets.

5.2.1 **Corticosteroids for tumor flare:** Swelling, erythema, and tenderness of lymph nodes (especially pathologically involved lymph nodes), with/without fever and rash, are expected effects of treatment with lenalidomide. First line treatment is analgesics (e.g. NSAIDs, acetaminophen, oral narcotics) or corticosteroids at the discretion of the treating physician. If the treating physician believes steroids are indicated, administration of dexamethasone (recommended dose = 4mg/day x 7 days) during the first two cycles of lenalidomide treatment is permitted. Steroid administration beyond 7 days can be considered after consultation with the principal investigator.

5.2.2 **Allopurinol:** All patients, unless allergic, should receive allopurinol 300 mg orally daily starting 3 days prior to initiating lenalidomide therapy and continuing through at least the end of the first cycle of treatment as tumor lysis syndrome prophylaxis. This coincides with Cycle 1 in Arm A and Cycle 4 in Arm B. Allopurinol may be continued through the second cycle of lenalidomide treatment and beyond at the discretion of the treating physician. If the patient is allergic to allopurinol, this drug will be omitted.

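### Section 9.3.3 defines dexamethasone exposure by the cycle before the PK draw in Arm A but by the cycle of the draw itself (Cycle 5) in Arm B

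*Combined protocol and SAP*

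**What the plan says.** Section 9.3.3 sets up a comparison among patients who had "dexamethasone treatment on cycles 1 (Arm A) or 5 (Arm B"). Its stated purpose is to detect an interaction through "steroid-induced induction of MDR1 or other lenalidomide clearance mechanisms". The sentence names no comparison group.

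The sampling times are in Section 9.3.1. In Arm A, "pharmacokinetic assessments of lenalidomide will occur during days 1 and 2 of cycle 2"; in Arm B, "PK sampling will occur during days 1 and 2 of cycle 5". Footnote s of the study calendar repeats both.

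Section 5.2.1 ties dexamethasone for tumor flare to lenalidomide exposure: its use "during the first two cycles of lenalidomide treatment is permitted". Table 2 turns this into cycle numbers. For Arm A: "Dexamethasone may be given for up to 7 days during Cycles 1 and 2 for symptomatic tumor flare". For Arm B: "Dexamethasone may be given for up to 7 days during Cycles 4 and 5 for symptomatic tumor flare". The text under Table 2 gives the starting dose "during the first cycle of treatment (Arm A: Cycle 1; Arm B: Cycle 4"), so Arm B begins lenalidomide three cycles after Arm A.

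**The concern.** Dexamethasone can alter a measured lenalidomide concentration only if it was given before or during sampling. The Arm A rule respects this, because Cycle 1 ends before the draw at the start of Cycle 2. The Arm B rule does not, because the draw takes up the first two days of Cycle 5 and the rest of that cycle comes afterwards. Cycle 4, when dexamethasone is also permitted and when any use precedes the draw, is not in the Arm B rule.

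At stake is whether the comparison can show what it is meant to show. Counting later use as exposure, and leaving out earlier use, both tend to hide a steroid effect on clearance.

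**Working it through.** The plan gives no test, power or sample size for this comparison, so there is no stated figure to reproduce. Two checks on timing apply.

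**1. Offset between arms (Arm B cycle minus Arm A cycle)**

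| Event | Source | Arm A | Arm B | Offset |
|---|---|---|---|---|
| First lenalidomide cycle | Table 2 | 1 | 4 | 3 |
| Earliest escalation | Text under Table 2 | 2 | 5 | 3 |
| Dexamethasone window, first cycle | Table 2 | 1 | 4 | 3 |
| Dexamethasone window, last cycle | Table 2 | 2 | 5 | 3 |
| Allopurinol, first lenalidomide cycle | 5.2.2 | 1 | 4 | 3 |
| PK draw | 9.3.1 | 2 | 5 | 3 |
| Dexamethasone grouping | 9.3.3 | 1 | 5 | **4** |

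The grouping rule is the only mismatch. Relative to the PK cycle, it sits at 1 − 2 = −1 in Arm A and 5 − 5 = 0 in Arm B. If prior exposure were meant, the pair would be 1 and 4; if exposure in the sampling cycle were meant, 2 and 5. Neither concept gives 1 and 5. With Cycle 4 in place of Cycle 5, the offset is 4 − 1 = 3 and the grouping cycle precedes the draw in both arms.

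**2. How much Arm B use falls after the draw**

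The documents give no dexamethasone start days, so each line below rests on an assumption. A start on Day 3 or later of Cycle 5 counts as after the draw.

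- Starts uniform over the 28 days of Cycle 5: (28 − 2)/28 = 26/28 = 93% after the draw.
- Starts confined to Days 1-8: (8 − 2)/8 = 6/8 = 75%.
- Front-loaded (geometric) starts with mean start day m: share = (1 − 1/m)². This gives 81% for m = 10, 64% for m = 5, 44% for m = 3 and 25% for m = 2. The share falls below one half when m is under 1/(1 − √0.5) = 3.4 days.
- Starts uniform over Cycles 4 and 5 with 7-day courses, any Cycle 5 dose counting as Cycle 5 use: the group holds the 28 Cycle 5 start days plus the last 6 of Cycle 4, so 26/34 = 76% had not begun by Day 2.

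For the Cycle 4 users left out: with uniform starts and 7-day courses, those starting on Days 1-22 have no Cycle 5 dose, which is 22/28 = 79%. If starts are confined to Days 1-8, it is all of them. Courses running from late Cycle 4 into Cycle 5 Day 1 would be classified correctly.

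**The case against.** The inconsistency itself is hard to contest, but three stronger readings are tempting and the documents do not support them.

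- *Nearly all Arm B exposure is misclassified, and that half of the comparison is uninformative.* A reader might infer this from 26 of 28 days following the draw. That is a share of days, not of patients. The text under Table 2 has patients seen on Days 1 and 8 of the first lenalidomide cycle and of any escalation cycle to look for lysis and flare, and Cycle 5 is the earliest escalation cycle in Arm B. Early starts are therefore possible, and with very early starts fewer than half of the courses would follow the draw.
- *Cycle 4 users are put in the wrong group.* This assumes a comparator of non-users, which 9.3.3 does not name. If Arm A users are compared with Arm B users, Cycle 4 users are omitted rather than misplaced. The rule fails to match the draw either way.
- *Replacing 5 with 4 secures exposure at sampling.* It secures prior exposure only. A 7-day course begun on Day 1 of Cycle 4 ends 28 − 7 = 21 days before the next cycle. The documents do not say whether any induction would last that long.

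It is also fair to say that the practical effect is small. Dexamethasone is optional, Section 13.5 plans mainly descriptive and graphical work on correlative markers, and Section 5.2 already has treatment dates recorded, so an analyst could classify by date. That limits the importance of the error. It does not make the written rule right, and no other section corrects it.

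**Conclusion.** The rule is wrong as written, and the matter is minor. The mismatch between 9.3.3 and 9.3.1 needs no assumption: Arm B use after Cycle 5 Day 2 counts as exposure although it cannot have affected the sample, and Cycle 4 use before the sample is omitted, or placed with the unexposed if the comparator is non-users.

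The size does rest on assumptions. The share of Cycle 5 courses starting after the draw ranges from 25% to 93% over the start-day patterns tried. It is a majority unless at least half of those courses start on Days 1-2. How many patients are involved cannot be worked out from the documents, though it is probably few. Neither the primary antibody endpoint nor the two-year CR analysis is affected.

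**What to change.** In 9.3.3, define exposure in both arms as any recorded dexamethasone from the first lenalidomide dose up to the PK draw, and compare these patients with those who had none in that interval. Because 5.2 asks for dates rather than times, add a line on how to class a course that starts on a sampling day. At the least, change the Arm B cycle from 5 to 4 and name the comparator, accepting that this captures prior rather than concurrent use.

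The cost is one or two sentences. The medication dates are already required under 5.2, so no new data are needed. Section 9 ends research sampling with protocol version 24, but the grouping can still be corrected at analysis. The change concerns analysis grouping only and alters nothing about how dexamethasone or lenalidomide is given.
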